1.3 Schema

The general study design is summarised in Figure 1. Please refer to Schedule of Activities (Section 1.1) for detailed information about the timing of protocol- required blood draws and laboratory tests.

Clinical Study Protocol - 6
Olaparib - ESR-18-13807

Figure 1 Study design

** If a patient is already on folic acid supplements and continues to experience folate deficiency and Hgb less than 10.0 g/dl, folic acid dose can be increased to 2 mg daily or higher, at the discretion of the investigator. A hematology consultation can be obtained if necessary.

INTRODUCTION

Investigators should be familiar with the current olaparib (AZD2281) Investigator Brochure (IB).

Olaparib (AZD2281, KU-0059436) is a potent Polyadenosine 5' diphosphoribose [poly (ADP ribose)] polymerisation (PARP) inhibitor (PARP-1, -2 and -3) that is being developed as an oral therapy, both as a monotherapy (including maintenance) and for combination with chemotherapy and other anti-cancer agents⁴.

PARP inhibition is a novel approach to targeting tumors with deficiencies in DNA repair mechanisms. PARP enzymes are essential for repairing DNA single strand breaks (SSBs). Inhibiting PARPs leads to the persistence of SSBs, which are then converted to the more serious DNA double strand breaks (DSBs) during the process of DNA replication. During the process of cell division, DSBs can be efficiently repaired in normal cells by homologous recombination repair (HR). Tumors with HR deficiencies (HRD)^{5,6,7} such as ovarian cancers in patients with *BRCA1/2* mutations, cannot accurately repair the DNA damage, which may become lethal to cells as it accumulates. In such tumor types, olaparib may offer a potentially efficacious and less toxic cancer treatment compared with currently available chemotherapy regimens.

BRCA1 and *BRCA2* defective tumors are intrinsically sensitive to PARP inhibitors, both in tumor models in vivo^{8,9} and in the clinic⁵. The mechanism of action for olaparib results from the trapping of inactive PARP onto the single-strand breaks preventing their repair^{10,11}. Persistence

Clinical Study Protocol - 6
Olaparib - ESR-18-13807

of SSBs during DNA replication results in their conversion into the more serious DNA DSBs that would normally be repaired by HR repair. Olaparib has been shown to inhibit selected tumor cell lines in vitro and in xenograft and primary explant models as well as in genetic *BRCA* knock-out models, either as a stand-alone treatment or in combination with established chemotherapies.

Initially, olaparib has been FDA approved for the treatment of advanced ovarian cancer¹². Later, the indications have expanded. Currently, it is approved for the following indications¹³⁻¹⁶

- First-Line Maintenance *BRCAm* Advanced Ovarian Cancer (*gBRCAm* = germline *BRCA*-mutated or *sBRCAm* = somatic *BRCA*-mutated)

- First-Line Maintenance HRD-Positive Advanced Ovarian Cancer in Combination with Bevacizumab. Homologous recombination deficiency (HRD) positive status defined by either a deleterious or suspected deleterious *BRCA* mutation, and/or genomic instability.

- Maintenance Recurrent Ovarian Cancer in patients who are in complete or partial response to platinum-based chemotherapy.

- Advanced *gBRCAm* Ovarian Cancer in patients who have been treated with 3 or more prior lines of chemotherapy.

- gBRCAm*, HER2-Negative Metastatic Breast Cancer

- First-Line Maintenance *gBRCAm* Metastatic Pancreatic Cancer whose disease has not progressed on at least 16 weeks of a first-line platinum-based chemotherapy regimen

- HRR Gene-mutated Metastatic Castration-Resistant Prostate Cancer in patients with deleterious germline or somatic homologous recombination repair (HRR) gene-mutated metastatic castration-resistant prostate cancer (mCRPC) who have progressed following prior treatment with enzalutamide or abiraterone .

Molecular sequencing of the tumor DNA is increasingly used in clinical practice to identify molecularly-targeted agents that can potentially effectively and safely treat patients with advanced cancers. Olaparib is used in this setting when solid tumors harbor molecular alterations such as germline and somatic mutations in *BRCA1* and *BRCA2* genes, other genes in Homologous DNA Recombination pathway, etc¹⁷. A detailed description of the chemistry, pharmacology, efficacy, and safety of olaparib is provided in the package insert.

1.4 Study rationale

See Section 1.2.

We have observed folate deficiency in 66% of patients of patients with advanced ovarian and metastatic breast cancer occurring within weeks of treatment initiation with olaparib^{2, 3}. While folate deficiency is a known cause of macrocytic anemia, it has not been previously reported in association with olaparib therapy. Since macrocytic anemia is a known complication of olaparib treatment regardless of the cancer type treated, folate deficiency can occur in these patients too.

Clinical Study Protocol - 6
Olaparib - ESR-18-13807

This study is conducted to assess the prevalence and timing of folate deficiency in patients with ovarian, breast, pancreatic, prostate, and other cancers that may benefit from olaparib as determined by their treating physicians based on their tumor sequencing or germline results. .

As folic acid supplementation has not been studied prospectively in this patient population, this study will also evaluate, in a randomized fashion, the impact of folic acid supplementation on anemia and need for transfusion as compared to a placebo group (i.e. no folic acid supplementation while on olaparib).

Background

Olaparib is generally well tolerated. For instance, in the clinical trial of maintenance olaparib monotherapy in patients with platinum-sensitive ovarian cancer who had had 2 or more lines of platinum-based chemotherapy (Study 19), adverse reactions led to olaparib dose interruption, reduction and discontinuation in 35 %, 26 %, and 6 % of patients, respectively¹³. Olaparib is known to cause hematologic toxicity. In the pooled analysis of multiple clinical trials, the following hematologic side effects were observed: anemia in 37% of patients, Macrocytosis (elevated mean corpuscular volume) is reported in up to 89% of patients treated with olaparib¹³. The manufacturer recommends monitoring blood counts at baseline and monthly thereafter, interrupting treatment until any hematologic toxicity has resolved to \leq grade 1, with additional evaluation if blood counts do not recover after 4 weeks of treatment interruption, including bone marrow and cytogenetic analyses^{5, 6}. Little is known about the etiology of olaparib-induced hematologic toxicity.

2. OBJECTIVES AND ENDPOINTS

Primary objective:

To determine the frequency and timing of folate deficiency in patients with solid tumors harboring molecular alterations such as germline and somatic mutations in *BRCA1* and *BRCA2* genes, other genes in Homologous DNA Recombination Repair (HRR) pathway, genomic stability as determined by Homologous Recombination Deficiency (HRD) assay, etc., who are treated with olaparib.

Secondary objectives:

To evaluate the effect of folic acid supplementation on serum folate, hemoglobin level, transfusion needs/number of transfusions, and need for olaparib treatment interruption, dose reduction and drug discontinuation.

To assess response rate (RR) to olaparib as it relates to serum folate level and folic acid supplementation.

Clinical Study Protocol - 6
Olaparib - ESR-18-13807

To assess progression-free survival (PFS) as it relates to serum folate level and folic acid supplementation.

Exploratory objectives:

To elucidate the mechanism of folate deficiency in patients treated with olaparib including possible interaction with germline *BRCA1* and *BRCA2* mutations via testing for folate receptors using immunohistochemistry on available paraffin embedded tumor samples from enrolled patients.

Primary endpoint:

The primary binary endpoint of the study is the percentage of patients who develop drug-induced folate deficiency, defined as serum folate level <7 ng/mL, within three months from start of olaparib therapy.

Secondary endpoints:

To assess the impact of folic acid supplementation on anemia, need for transfusion, and olaparib treatment interruption, dose reduction and drug discontinuation as compared to those who did not receive/require folic acid supplementation

To determine tumor response rate (RR), using treating physician assessment, on olaparib therapy in patients who develop folate deficiency and receive folic acid supplementation as compared to those who do not receive/require folic acid supplementation. Will also compare RR to historical controls (patients with solid tumors treated with olaparib or other approved agents on clinical trials).

To determine progression-free survival (PFS), using treating physician assessment based on olaparib therapy in patients who develop folate deficiency and receive folic acid supplementation as compared to those who do not receive/require folic acid supplementation. Will also compare PFS to historical controls (patients with solid tumors treated with olaparib or other approved agents on clinical trials) using published data.

Exploratory Endpoints:

To evaluate association between:

- *BRCA 1*, *BRCA 2*, and other HRR gene status (germline mutation carrier vs non-carrier) and the intensity of folate receptor alpha expression in the tumor ($<50\%$ or $>50\%$)
- *BRCA 1*, *BRCA 2*, and other HRR gene status (germline mutation carrier vs non-carrier) and nadir serum folate level during olaparib treatment

Clinical Study Protocol - 6
Olaparib - ESR-18-13807

- *BRCA 1*, *BRCA 2*, and other HRR gene status (germline mutation carrier vs non-carrier) and tumor response in patients receiving folate supplementation as compared to patients not receiving folate supplementation and historical controls
- Folate deficiency and expression of folate receptors in patients' tumor samples

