1.2 Synopsis

Protocol Title: A study of serum folate levels in patients treated with olaparib

Rationale:

Olaparib as well as other PARP inhibitors are known to cause hematologic toxicity, most commonly, macrocytic anemia regardless of the cancer type treated. The development of anemia may lead to blood transfusions, dose reductions and delay as well as drug discontinuation¹. The cause of anemia is poorly understood. We have observed folate deficiency (<7 ng/mL) in 66% of patients treated with olaparib in a small group of patients with advanced ovarian and metastatic breast cancer occurring within weeks of treatment initiation with olaparib^{2,3}. Folate deficiency is a known cause of macrocytic anemia. However, it has not been previously reported in association with olaparib therapy. In our cohort of patients, folic acid replacement allowed us to avoid or decrease the need for blood transfusions, olaparib dose reduction and discontinuation of therapy.

Statistical methods:

[figure not shown]
A previous study by Rush investigators observed folate deficiency (<7 ng/mL) in 66% of patients treated with olaparib^{2,3}. Under this framework, a sample size of n=60 is calculated using one-sided test to have 80% power in detecting more than half (50%) of the patients having folate deficiency at 0.05 significance level. Allowing for 20% attrition, we propose a sample size of n=75 for this study. The statistical analysis will provide descriptive summaries of the primary endpoint of drug-induced folate deficiency as well the endpoint of response rate and other secondary endpoints. The significance of the observed percentage of folate-deficient cases will be assessed by statistical hypothesis test, as well as by multivariable analysis of the binary endpoint of folate deficiency adjusted by important covariates. The secondary endpoint of response rate to olaparib will be compared between the group who develop cytopenias, folate deficiency, and receive folic acid supplementation and the comparator group by descriptive summaries as well as by statistical hypothesis test. Statistical analysis will be performed in the R Statistical software. No adjustment for multiplicity will be made. Even though the sample size of 75 is optimal to achieve primary and secondary objectives, it would be reasonable to initially accrue 30 patients and re-evaluate the need for continued accrual based on the percentage of patients who develop folate deficiency in this first phase.

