8.4 Statistical analyses

8.4.1 Efficacy analyses

Patients will be monitored for development of anemia and folate deficiency at scheduled time points throughout the course of the study, as described in Section 1.1. Patients who develop \leq G2 cytopenias and folate deficiency will be randomly assigned in a 1:1 ratio to receive folic acid supplementation 1 mg daily or no supplementation. Patients who develop G3 or higher cytopenias and folate deficiency will be started on folic acid supplementation, thus not included in the randomization. For patients who are randomized, we will assess the impact of folic acid supplementation on anemia, need for transfusion, and dose interruption, dose reduction and drug discontinuation of olaparib as compared to those who did not receive/require folic acid supplementation. Additionally, PFS and RR to olaparib will be compared amongst randomized patients relative to folic acid supplementation.

The statistical analysis will provide descriptive summaries as well as 95% confidence intervals for the primary endpoint of drug-induced folate deficiency in addition to response rate and other secondary endpoints. Kaplan-Meier methodology will be used to estimate the PFS curve and estimate of median PFS and corresponding 95% confidence interval will be provided. The significance of the observed percentage of folate-deficient cases will be assessed by statistical hypothesis test, as well as by multivariable analysis of the binary endpoint of folate deficiency adjusted by important covariates. Covariates will include age, race/ethnic group, previous therapy, Hgb prior to olaparib therapy, genetic testing result (*BRCA* carrier status). RR and PFS will be compared to historical controls as a descriptive comparison. Analyses will be reported on the entire combined cohort of patients with solid tumors and also separately for each cancer type. The statistical analysis of the exploratory endpoint will be specified in the SAP. Statistical analysis will be performed in the R Statistical software. No adjustment for multiplicity will be made.

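### Response and PFS are to be related to serum folate level, but no analysis does so, and the endpoint contrast merges folate status, folic acid and anaemia into one class

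*Combined protocol and SAP*

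**What the plan says.** Two secondary objectives in Section 2 each name two exposures: "To assess response rate (RR) to olaparib as it relates to serum folate level and folic acid supplementation" and "To assess progression-free survival (PFS) as it relates to serum folate level and folic acid supplementation".

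The secondary endpoints in the same section turn these into one contrast. Response and PFS are to be determined "in patients who develop folate deficiency and receive folic acid supplementation as compared to those who do not receive/require folic acid supplementation". The synopsis (Section 1.2) adds cytopenias to the class and attaches a hypothesis test for response "between the group who develop cytopenias, folate deficiency, and receive folic acid supplementation and the comparator group".

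Section 8.4.1 adds a randomised comparison. Eligible deficient patients "will be randomly assigned in a 1:1 ratio to receive folic acid supplementation 1 mg daily or no supplementation", and "PFS and RR to olaparib will be compared amongst randomized patients relative to folic acid supplementation". Under Section 3.1, a randomised patient whose haemoglobin falls below 10 g/dl while deficient receives folic acid whatever the assigned arm.

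Section 7.1.1 counts PFS from enrolment. Section 1.1 schedules serum folate every two weeks for three months and then monthly to month 6. Section 3.4 ends the study at 7 months.

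**The concern.** Half of each objective, the part about folate level, has no analysis. The contrast that stands in for it is hard to interpret. A patient enters the class by becoming deficient, by having haemoglobin low enough to trigger randomisation or supplementation, and by receiving folic acid. A difference from the comparator could come from any of these, and opposing effects could cancel.

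Section 8.1 lists the hypothesis that folate replacement leaves the antitumour effect of olaparib unchanged. A diluted contrast tends towards no difference, which could be misread as support for that hypothesis.

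Class membership also depends on the future. PFS starts at enrolment, but a patient must stay in follow-up long enough to be found deficient and supplemented. Early progressions and deaths therefore fall in the comparator.

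**Working it through.** **1. Planned analyses of response and PFS, side by side**

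| Place | Contrast | Uses folate level? |
|---|---|---|
| Section 2, objectives | folate level, and folic acid | yes, as a question |
| Section 2, endpoints | deficient and supplemented v. not receiving or requiring folic acid | only as a cut, tied to treatment |
| Section 1.2, response test | cytopenia, deficiency and supplementation v. comparator | same |
| Section 8.4.1, randomised patients | by folic acid | no; all are deficient at entry |
| Sections 2 and 8.4.1, historical controls | treated patients v. published data | no |

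Elsewhere, the multivariable model in Section 8.4.1 has deficiency as its outcome, and nadir folate (Section 2, exploratory) is related only to gene status.

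**2. Who is in the comparator.** Take the 60 evaluable patients and 66% deficiency of Section 8.2: 0.66 × 60 = 39.6 deficient and 20.4 not. The supplemented share is not given, so it is assumed.
- One half supplemented: class 19.8, comparator 40.2, of whom 19.8 (49%) are deficient.
- Two thirds supplemented: class 26.4, comparator 33.6, of whom 13.2 (39%) are deficient.
- If only 37% of deficient patients were anaemic (the pooled anaemia rate in the Background text, borrowed here) and these were randomised 1:1: class 39.6 × 0.37 × 0.5 = 7.3, comparator 52.7, of whom 32.3 (61%) are deficient.

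If deficiency alone drove response, a true 30-point difference would appear in the class contrast as 30 × 20.4/40.2 = 15 points in the first case and 30 × 20.4/52.7 = 12 points in the third.

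**3. Timing.** With sampling every two weeks and a confirmatory draw two weeks after the first low value (Section 1.1), a patient reaches the class by the confirmed route no earlier than about 2 + 2 = 4 weeks, and possibly as late as month 6 of a 7-month study. Progression before then cannot count against the class.

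**4. The plan's own sample size.** For 66% against 50%, one-sided 0.05 and 80% power, the normal approximation is n = [1.645 × 0.5 + 0.842 × √(0.66 × 0.34)]² / 0.16² ≈ 58. The exact binomial at n = 60 (reject at 37 or more) has size 0.046 and power 0.802, and 60/0.80 = 75. The stated figures reproduce, but they cover only the primary endpoint.

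**5. Information about folate level kept by the class (illustration).** Assume log folate is normal (z), its effect is linear, folic acid has no effect, and a share s of deficient patients is supplemented at random. With q = 0.66s and φ(0.412) = 0.3664, corr² = (0.3664/0.66)² × q/(1 − q) = 0.308 × q/(1 − q).
- s = 1/2: q = 0.33, corr² = 0.15.
- s = 2/3: q = 0.44, corr² = 0.24.
- s = 1 (a clean deficiency cut): q = 0.66, corr² = 0.60.

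If supplementation instead picked out exactly the lowest-folate 33%, the class would keep φ(0.440)²/(0.33 × 0.67) = 0.59. The 1:1 allocation step keeps the true figure below that bound.

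**6. Opposing effects.** In a simulation of 60 patients (800 runs per setting, 37% or 100% of deficient patients anaemic and randomised 1:1), with assumed response odds ratios of 2 per SD of folate and 2.5 for folic acid, the class contrast was significant in about 7% of runs by Fisher's test and 9% to 12% by likelihood ratio, although both effects were real.

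**The case against.** The strongest reply is that the folic acid question is already handled. Section 8.4.1 compares response and PFS among randomised patients, all deficient, which isolates supplementation. The only tumour-outcome hypothesis in Section 8.1 concerns replacement, not folate level. The study is a pilot powered for the primary endpoint alone. This stands. It rules out a stronger reading that a reader might infer from the endpoints, that folate and folic acid effects cannot be separated anywhere in the plan. What limits the randomised comparison is its size and the crossover below 10 g/dl.

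A reader might also turn step 5 into a power statement. Against a hypothetical 80% for the continuous level, 15% and 24% of the information correspond to power of about 19% and 28%. The documents do not support this as a property of the trial. They give no power, effect size or event count for response or PFS, and no supplemented share. Supplementation is also not random with respect to folate depth if, as the synopsis rationale holds, deficiency causes anaemia.

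Finally, regressing response on screening folate would not repair the gap. Exclusion 1 in Section 4.2 removes patients below 7 ng/mL, so screening values are truncated and precede the drug-induced fall under study.

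None of these replies supplies an analysis by folate level or makes the class test interpretable.

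**Conclusion.** The mismatch between objectives and endpoints holds on the text alone. Response and PFS are never related to folate level. The contrast given a test in the synopsis confounds folate status, folic acid and anaemia, has deficient patients (such as randomised controls) in its comparator, and classifies patients by events after the PFS origin. Folic acid itself is addressed by the randomised comparison, subject to crossover.

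The size is illustrative: about 15% to 24% of the folate information is kept if one half to two thirds of deficient patients are supplemented at random and 66% are deficient, and more if supplementation tracks low folate.

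Class membership is also uncertain because the rules conflict. Section 1.1 randomises confirmed deficiency with haemoglobin between 10 and 12 g/dl and gives folic acid without randomisation below 10. Section 3.1 states randomisation below 12 g/dl. Section 8.4.1 randomises cytopenias up to grade 2 and supplements from grade 3, while Table 8 places haemoglobin from 8 to below 10 g/dl in grade 2. Section 5.6 starts folic acid in patients with deficiency and states no haemoglobin condition. These passages must be reconciled. Until they are, it is unclear whether deficient patients without anaemia belong to the class or to its comparator.

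**What to change.** Change Sections 1.2, 2 and 8.4.1 together.

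(a) Folic acid: base inference for response and PFS on the randomised arms as assigned. Show the combined class descriptively, without a test.

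(b) Folate level: add an analysis labelled exploratory and reported as estimates with confidence intervals. For PFS, use a Cox model with time-updated log serum folate from the scheduled samples, time-updated folic acid and time-updated haemoglobin. Because supplementation is expected to raise folate, the folic acid term in that model is not its total effect, so that question stays with (a). For response, use a logistic model on on-treatment folate before any supplementation, for example at a fixed landmark, rather than on screening folate.

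(c) If no folate-level analysis is intended, remove folate level from the two objectives.

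(d) Reconcile the passages on who is randomised and who receives folic acid, so that group membership is defined once.

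The cost is protocol and SAP wording plus two models on data already scheduled, with no new visits or samples. The downside is that the folate-level result is observational and will be imprecise at 60 to 75 patients and 7 months. A landmark also loses patients who are supplemented or progress before it.

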3. STUDY DESIGN

3.1 Overall design

This is a pilot, multi-center study evaluating the prevalence and timing of folate deficiency in patients with advanced solid tumors who are eligible to receive olaparib.

If patients develop folate deficiency concomitantly with a Hgb less than 12.0 g/dl (grade 1), they will then be randomized to receive either a placebo or folate supplementation.

All randomized patients who develop a Hgb less than 10 g/dl (grade 2) concomitantly with folate deficiency will receive folic acid supplementation irrespective of their prior randomization. If such patients were originally randomized to receive folic acid and continue to have a Hgb less than 10 g/dl and folate deficiency despite folate supplementation, folic acid dose will be increased to 2 mg daily or higher at the discretion of the investigator.

Patients will continue with olaparib until objective disease progression (determined by treating physician assessment) as long as in the Investigator's opinion they are benefiting from treatment and they do not meet any other discontinuation criteria.

For an overview of the study design see Figure 1, Section 1.3. For details on treatments given during the study, see Section 5.1 Treatments Administered.

For details on what is included in the efficacy and safety endpoints, see Section 2 Objectives and Endpoints.

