5.3 Measures to minimise bias: randomisation and blinding

If a patient withdraws from the study, then his/her enrolment/randomisation code cannot be reused. Withdrawn patients will not be replaced

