7. STUDY ASSESSMENTS AND PROCEDURES

7.1 Efficacy assessments

7.1.1 Clinical outcome assessments

Evaluate the percentage of patients who develop drug-induced folate deficiency while on olaparib, defined as serum folate level <7 ng/mL.

Determine the impact of folic acid supplementation on anemia, need for transfusion, and dose modification of olaparib as compared to those who did not receive/require folic acid supplementation.

Tumor assessment will be performed as per treating physician's decision and would include regular clinical exams, tumor marker monitoring, and imaging (body CT scans) at every 3 -6 month interval. Tumor response will be evaluated according to treating physician assessment. Response rate is defined as achievement of complete response (CR) or partial response (PR). Progression free survival, PFS, is defined as time from enrolment until disease progression or death. Patients who withdrew from olaparib before disease progression or death will be censored at the date of their last tumor assessment.

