7.4.4.1 Management of haematological toxicity

7.4.4.2 Management of anaemia

Table 8 Management of anaemia

Haemoglobin	Action to be taken
Hgb < 10 but ≥ 8 g/dl (CTCAE Grade 2)	
First occurrence: Give appropriate supportive treatment and investigate causality. Investigator judgement to continue olaparib with supportive treatment (e.g., transfusion) or interrupt dose for a maximum of 4 weeks. Study treatment can be restarted if Hb has recovered to > 9g/dl.
 
Subsequent occurrences: If Hgb < 10 but ≥ 9 g/dl investigator judgement to continue olaparib with supportive treatment (e.g., transfusion) or dose interrupt (for max of 4 weeks) and upon recovery dose reduction may be considered (to 250 mg twice daily as a first step and to 200 mg twice daily as a second step). If Hgb < 9 but ≥ 8 g/dl, dose interrupt (for max of 4 weeks) until Hb ≥ 9 g/dl and upon recovery dose reduction may be considered (to 250 mg twice daily as a first step and to 200 mg twice daily as a second step).

Hgb < 8 g/dl (CTCAE Grade 3)	
Give appropriate supportive treatment (e.g., transfusion) and investigate causality. Interrupt olaparib for a maximum of 4 weeks until improved to Hgb ≥ 9 g/dl. Upon recovery dose reduce to 250 mg twice daily as a first step and to 200 mg twice daily as a second step in the case of repeat Hgb decrease.

Common treatable causes of anemia (e.g., iron, vitamin B12 or folate deficiencies and hypothyroidism) should be investigated and appropriately managed. In some cases management of anemia may require blood transfusions. For cases where patients develop prolonged haematological toxicity (≥2 week interruption/delay in study treatment due to CTC grade 3 (Hgb less than 8.0 g/dl) or worse anemia and/or development of blood transfusion dependence), refer to guidance later in this section for the management of this.

Clinical Study Protocol - 6
Olaparib - ESR-18-13807

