8.3 Populations for analyses

Clinical Study Protocol - 6
Olaparib - ESR-18-13807

All enrolled patients who receive at least one dose of olaparib will be included in the analysis population to be used to assess the efficacy and safety endpoints.

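### For anaemia, transfusion and olaparib dosing, the comparator is defined by folic acid use or need and not by assigned arm, so rescued controls fall out of the control group

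*Combined protocol and SAP*

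**What the plan says.** Section 1.4 states the aim of the randomised part: to evaluate, "in a randomized fashion, the impact of folic acid supplementation on anemia and need for transfusion as compared to a placebo group". It then describes that placebo group as having no folic acid while on olaparib.

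The comparator is worded differently where the endpoints are defined. Section 2 lists anaemia, transfusion, olaparib interruption, "dose reduction and drug discontinuation as compared to those who did not receive/require folic acid supplementation". Section 7.1.1 repeats it: "dose modification of olaparib as compared to those who did not receive/require folic acid supplementation". Neither is limited to randomised patients. Section 8.4.1 does limit this comparison to randomised patients, with 1:1 allocation, but keeps the same comparator.

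Section 3.1 provides that randomised patients whose Hgb falls below 10 g/dl "concomitantly with folate deficiency will receive folic acid supplementation irrespective of their prior randomization".

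Two sections could have settled how such patients are grouped. Section 5.3, on bias, says only that after withdrawal "his/her enrolment/randomisation code cannot be reused" and that withdrawn patients are not replaced. Section 8.3 gives a single set: "All enrolled patients who receive at least one dose of olaparib will be included in the analysis population". It defines no randomised set.

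For response rate (RR) and progression-free survival (PFS), Section 8.4.1 compares randomised patients according to folic acid supplementation without saying whether assigned or received. Section 7.1.1 says PFS "is defined as time from enrolment until disease progression or death". The Synopsis (1.2) plans an RR test against a comparator group that it does not define.

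**The concern.** A control given folic acid under Section 3.1 has both received and required it. On the wording of Sections 2, 7.1.1 and 8.4.1, that patient is no longer a comparator, and nothing says whether the patient is moved to the folic acid group, dropped, or kept in the assigned arm.

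This matters because the reason for the switch is bound up with the outcomes. The trigger is Hgb below 10 g/dl with folate deficiency, which is itself an anaemia outcome. From the same Hgb level, Table 8 lists "Investigator judgement to continue olaparib with supportive treatment (e.g., transfusion", with interruption of olaparib as the alternative. Grouping by receipt therefore selects on the outcome: the controls left in the comparator are those who did not deteriorate. The second hypothesis in Section 8.1, that folic acid mitigates olaparib's haematologic toxicity, rests on these outcomes, so the grouping could decide the direction of the answer.

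**Working it through.** **The plan's own figure.** An exact one-sample binomial test with null 50%, alternative 66%, n = 60 and success at 37 or more has one-sided alpha 0.046 and power 80.2%. Attrition: 60/(1 − 0.20) = 75. Both figures in Section 8.2 reproduce. They cover only the primary endpoint and do not depend on this point. No sample size is stated for the randomised comparison. At the planning rate, 0.66 × 75 = 49.5 deficient patients, or about 25 per arm before the Hgb condition for randomisation is applied.

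**Model.** The documents give no transfusion or trigger rates, so the rates below are assumptions. Allocation is 1:1, as in Section 8.4.1.

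- qf, qc: share meeting the trigger in the folic acid and control arms (0 to 40%).
- t = 0.5: share of triggered patients transfused.
- b = 0, 0.1 or 0.2: share of non-triggered patients transfused, including controls with Hgb below 10 g/dl but normal folate.

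By arm:
- folic acid = qf·t + (1 − qf)·b
- control = qc·t + (1 − qc)·b

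By receipt, with triggered controls moved to the folic acid group:
- received = [qf·t + (1 − qf)·b + qc·t]/(1 + qc)
- not received = b
- difference = (qf + qc)(t − b)/(1 + qc)

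Arm size cancels. If folic acid does not alter b, the difference is above zero for every qf whenever t > b and qc > 0.

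Worked example, qf = 0.2, qc = 0.4, b = 0.1:
- folic acid arm: 0.10 + 0.08 = 0.18
- control arm: 0.20 + 0.06 = 0.26
- received: (0.18 + 0.20)/1.4 = 0.271
- not received: 0.10

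Percentage transfused, for b = 0 / 0.1 / 0.2:

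| Case | By arm: folic acid vs control | By receipt: received vs not |
|---|---|---|
| No effect, 40% trigger | 20 vs 20 / 26 vs 26 / 32 vs 32 | 28.6 vs 0 / 32.9 vs 10 / 37.1 vs 20 |
| No effect, 20% trigger | 10 vs 10 / 18 vs 18 / 26 vs 26 | 16.7 vs 0 / 23.3 vs 10 / 30.0 vs 20 |
| Triggers halved, 20% vs 40% | 10 vs 20 / 18 vs 26 / 26 vs 32 | 21.4 vs 0 / 27.1 vs 10 / 32.9 vs 20 |
| All triggers prevented, 0% vs 40% | 0 vs 20 / 10 vs 26 / 20 vs 32 | 14.3 vs 0 / 21.4 vs 10 / 28.6 vs 20 |

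The 0% entries under receipt follow from assuming b = 0.

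**If rescued controls are dropped instead of moved.** The folic acid arm is compared with b, so the difference is qf·(t − b), which is never below zero. With b = 0.1, halved triggers give 18% vs 10%. With all triggers prevented, the result is 10% vs 10%, and the true 10% vs 26% benefit disappears.

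**Second set of assumed risks.** With no effect, t = 0.5 and b = 0.05, trigger shares of 10, 20, 30, 40 and 50% give a spurious excess against folic acid of 8, 15, 21, 26 and 30 points if rescued controls are moved. If they are dropped, the excess is 4.5, 9, 13.5, 18 and 22.5 points.

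**If folic acid also halves b in its own arm.**
- qf = 0.2, qc = 0.4, b = 0.1: by arm 14% vs 26%; by receipt (0.14 + 0.20)/1.4 = 24.3% vs 10%.
- qf = 0.2, qc = 0.4, b = 0.2: by arm 18% vs 32%; by receipt (0.18 + 0.20)/1.4 = 27.1% vs 20%.
- qf = 0.1, qc = 0.2, b = 0.2: by arm 14% vs 26%; by receipt (0.14 + 0.10)/1.2 = 20% vs 20%.
- qf = 0, qc = 0.2, b = 0.2: by arm 10% vs 26%; by receipt (0.10 + 0.10)/1.2 = 16.7% vs 20%.

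In the last two the benefit is erased or much reduced, but not reversed.

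**The case against.** The strongest reply is that the plan never orders a by-receipt analysis. Section 1.4 promises a randomised evaluation, Section 8.4.1 confines the comparison to randomised patients allocated 1:1, and no section reclassifies anyone. A by-arm reading is possible. But the restriction in Section 8.4.1 fixes who is compared, not how they are grouped, and the same sentence brings back the comparator defined by receipt or need. Section 1.4 itself describes placebo as no folic acid.

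Several narrower points stand as limits:

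- All transfusion and trigger rates are assumed, and only transfusion is modelled. Table 8 leaves transfusion to the investigator's judgement at Hgb 8 to 10 g/dl.
- Reversal is not universal, as the last two variants show.
- The trigger has two parts. Folic acid could lower qf by correcting serum folate alone, so fewer triggers need not mean less anaemia.
- About 25 per arm is a planning figure, not a hard ceiling. The 66% comes from a small cohort, and deficiency can be identified throughout six months of monitoring.
- This is a pilot study, and these are unpowered secondary endpoints.

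There is also a separate conflict. Section 1.1 randomises at Hgb between 10 and 12 g/dl and not below 10. Section 8.4.1 randomises cytopenias up to grade 2, and Table 8 places grade 2 at Hgb 8 to 10 g/dl. These passages must be reconciled because they decide who can become a rescued control, but they do not answer this point.

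**Conclusion.** The concern holds: the comparator is wrong as written for a randomised comparison. Followed literally, it removes controls on an outcome-linked trigger. If folic acid has no effect, this produces an apparent excess against it whether rescued controls are moved or dropped. With a 40% trigger rate and the main inputs, the spurious excess from moving them is 17 to 29 points (37.1 − 20 to 28.6 − 0). If folic acid truly reduces triggers, the benefit is reversed in every tabulated case, and reduced, erased or reversed if folic acid also lowers background transfusion. These are directions of bias on assumed inputs, not predicted results; the plan names no test for transfusion.

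The primary endpoint and n = 60/75 are unaffected. No size or direction of bias is shown for RR or PFS, where the problem is only that the grouping and the start date are not stated for the randomised comparison. The point should be settled before any outcomes are compared.

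**What to change.** - **Sections 2, 7.1.1 and 8.4.1:** for anaemia, transfusion and olaparib dosing, replace the receive/require comparator with patients randomised to the control arm.
- **Section 8.3:** add an all-randomised set, analysed in the assigned arm regardless of later folic acid, with these outcomes counted from randomisation.
- **Section 8.4.1, RR and PFS:** state that the randomised comparison is by assigned arm. Give the PFS start date for that comparison and reconcile it with the enrolment start in Section 7.1.1. Enrolment can remain the start for the whole-cohort PFS estimate.
- **Section 1.2:** define the comparator group for the RR test as the assigned control arm, or make that contrast descriptive.
- **Other contrasts:** keep comparisons by receipt, or with never-randomised or never-deficient patients (including the RR and PFS exposure comparisons in Section 2), as separate descriptive summaries.

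The cost is wording only. No visits or tests are added, and the rescue rule is untouched. The by-arm comparison will be small. It estimates folic acid at randomisation against folic acid only after Hgb falls below 10 g/dl with deficiency, so any effect may be diluted; the plan should say so.
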